#### 1.1.2 Number of Subjects and Randomization

Approximately 30 adult female subjects will be randomized 1:1 to receive either *Sculptra* reconstituted with 8 mL SWFI with the addition of 1 mL 2% lidocaine HCl or *Sculptra* reconstituted with 17 mL SWFI with the addition of 1 mL 2% lidocaine HCl. Subjects will be stratified by GDS severity score and study center. Randomization numbers will be allocated in ascending sequential order to each subject.

	Title 43USSA2112 Statistical Analysis Plan - Sculptra Decolletage US Pilot	Doc id MA-55694
--	--	---------------------------

## 1.2 Study Objectives and Endpoints

### 1.2.1 Primary Effectiveness Objective and Endpoint

The primary objective of the study is to evaluate the effectiveness of *Sculptra* for correction of wrinkles in the décolletage area. The primary endpoint is the percentage of responders, defined by at least one grade improvement from baseline, on the GDS, as assessed live by the Treating Investigator, at Month 9 for each treatment group.

### 1.2.2 Secondary Effectiveness Objectives and Endpoints

To evaluate the effectiveness of *Sculptra* for correction of wrinkles in the décolletage area the following endpoints will be used:

1. Percentage of responders, defined by at least one grade improvement from baseline, on the GDS, as assessed live by the Treating Investigator, at Month 6.
2. Percentage of responders, defined by having at least “Improved” (improved, much improved or very much improved) according to the Global Aesthetic Improvement Scale (GAIS), as assessed by the subject and the Treating Investigator separately, at Month 6 and 9.

CCI

### 1.2.4 Safety Objectives and Endpoints

The safety objectives and endpoints are as follows:

- To evaluate the incidence, intensity, time to onset, and duration of adverse events (AEs) collected throughout the study period.
- Incidence, intensity, time to onset and number of days of pre-defined expected post-treatment events collected using subject diaries for 28 days from each treatment.

GALDERMA <small>EST. 1981</small>	Title 43USSA2112 Statistical Analysis Plan - Sculptra Decolletage US PiLot	Doc id MA-55694
---	---	----------------------------------

Effective date: 2023-03-06 14:53

*Effective*

Version: 1.0

### 1.3 Effectiveness Assessments

For all assessments, baseline will be defined as the observation that is closest to but prior to study treatment on Day 1. Change from baseline will be calculated as the value at a given time point minus the baseline value.

#### 1.3.1 Galderma Décolletage Scale (GDS)

The GDS is a 5-point validated scale used to assess lines and wrinkles. The scale assessment will be performed live by the Treatment Investigator at all visits.

CCI

#### 1.3.2 Global Aesthetic Improvement Scale (GAIS)

The 7-grade GAIS will be used to assess the aesthetic improvement of the décolletage live by the Treating Investigator and the subject, independently of each other, by comparison to a photograph taken at the baseline visit before the first treatment. The GAIS will be assessed at 1 month following each treatment, 6 and 9 months after baseline.

CCI

GALDERMA EST. 1981	Title 43USSA2112 Statistical Analysis Plan - Sculptra Decolletage US PiLot	Doc id MA-55694
------------------------------	---	----------------------------------

Effective date: 2023-03-06 14:53

Effective date:

CCI

[REDACTED]	[REDACTED]

CCI

*Effective*

Version: 1.0

GALDERMA <small>EST. 1981</small>	Title 43USSA2112 Statistical Analysis Plan - Sculptra Decolletage US PiLot	Doc id MA-55694
---	---	----------------------------------

## 1.4 Safety Assessments

The methods for collecting safety data are described in Section 7 of the protocol. Data to be collected include the following:

- Adverse events.
- Subject diaries to be completed daily for 28 days following each treatment session with direct questioning for the following pre-identified symptoms: pain, tenderness, redness, bruising, swelling, itching, and other.
- Urine pregnancy test for women of childbearing potential performed at screening and all treatment visits (prior to treatment).
- **CCI** [REDACTED]
- **CCI** [REDACTED]
- Device deficiencies assessed at all treatment visits.

## 2 Statistical Methods

### 2.1 General Methods

Any change made to the finalized SAP before database lock will result in an SAP amendment. Otherwise, changes will be documented in the Clinical Study Report (CSR). However, if additional supportive or exploratory analyses are requested after SAP approval, this will not require amendment of the SAP, but these additional analyses will be described in the CSR.

Some of the analyses detailed here may be more explicit or in some respects different from those stated in the protocol. In case of differences, this SAP supersedes the statistical sections in the protocol.

#### 2.1.1 Programming Conventions

**CCI** [REDACTED] will have responsibility for performing analyses. All computations for statistical analyses will be performed using SAS® software, Version 9.4 or later. All SAS programs used in the production of statistical summary outputs will be validated with independent programming prior to finalization. In addition, all program outputs will be independently reviewed. The validation process will be used to confirm that all data manipulations and calculations were accurately done. Once validation is complete, a senior statistical reviewer will perform a final review of the documents to ensure the accuracy and consistency with this plan and consistency within tables. Upon completion of validation and quality review procedures, all documentation will be collected and filed by the project statistician or designee.

The electronic case report form (eCRF) data for all subjects will be included in the analysis datasets that are prepared for use in table and figure production.

 GALDERMA EST. 1981	Title 43USSA2112 Statistical Analysis Plan - Sculptra Decolletage US Pilot	Doc id MA-55694
---	--	---------------------------

Effective date: 2023-03-06 14:53

Effective

Version: 1.0

## 2.1.2 Reporting Conventions

The formats for the tables, listings, and figures described in this SAP will be provided in a companion document. Changes to the formats of these reports that are decided after the finalization of the SAP will not require an amendment. In addition, any additional supportive or exploratory analyses requested after SAP approval will not require amendment of the SAP. These additional analyses will be described in the CSR.

Study data from the eCRFs as well as derived variables will be provided in subject data listings. An indication of specific listings for each data type will not be indicated in the text of subsequent SAP sections. Data listings supplied as part of the CSR will be sorted by study site number concatenated with subject number, treatment group, assessment dates, and/or time point.

The following conventions will be applied to all data presentations and analyses:

- Confidence intervals (CIs) will be two-tailed and constructed at a confidence level of 95%. Statistical tests will be performed at a significance level of 5%, and p-values will be two-sided, unless otherwise specified.
- Quantitative variables will generally be summarized by the number of subjects, mean, standard deviation, median, minimum, and maximum. Unless otherwise specified, the minimum and maximum values will be displayed to the same number of decimal places as the raw data, the mean and median will be presented to one extra decimal place compared to the raw data, and the standard deviation will be displayed to two extra decimal places compared to the raw data.
- Categorical variables will be summarized by the number and percentage of subjects (and number of events where appropriate) within each category. Unless otherwise specified, the percentage will be presented in parentheses to one decimal place. Frequency and percentage values of 0 will be presented as '0' rather than '0 (0)'.
- All summary tables will include the analysis population sample size (i.e., number of subjects) in each treatment group.
- Date variables will be formatted as DDMMMYYYY for presentation.

## 2.2 Analysis Populations

The statistical analyses will be performed based on the following subject populations.

### 2.2.1 Safety Population

The Safety population includes all subjects who were treated with *Sculptra*. Subjects are analyzed according to the treatment received.

### 2.2.2 Intent-to-Treat (ITT) Population

The ITT population includes all subjects who were randomized, and will be analyzed according to the randomization scheme. All effectiveness variables will be analyzed based on the ITT population.

 GALDERMA EST. 1981	Title 43USSA2112 Statistical Analysis Plan - Sculptra Decolletage US Pilot	Doc id MA-55694
---	--	---------------------------

### 2.2.3 Per-Protocol (PP) Population

The PP population includes all ITT subjects who complete the visit 9 months after baseline, and are without any deviations considered to have substantial impact on the primary effectiveness outcome. If the PP population contains less than 90% of the subjects in the ITT, a sensitivity analysis of the primary effectiveness endpoint will be performed based on the PP population.

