9.1 General

A comprehensive Statistical Analysis Plan (SAP) with a detailed description of all statistical analyses will be developed.

All study data will be listed in subject data listings.

	Title 43USSA2112 CIP Sculptra Decolletage	Doc id
GALDERMA EST. 1981	•	MA-50966

All statistical analyses, including summary tables and data listings, will be performed using SAS. Confidence intervals will be two-sided and constructed at a confidence level of 95%.

All endpoints will be summarized descriptively. Continuous endpoints will be summarized using mean, median, standard deviation (SD), minimum and maximum values, for the observed value as well as the change from baseline. Categorical endpoints will be presented in frequency tables with number and percentage of observations for each level.

9.2 **Analysis populations**

The following populations will be defined:

•	Safety	Includes	all	subjects	who	were	treated	with	Sculptra.
	•	Subjects	are a	analyzed l	based	on the	as treate	ed prir	nciple (i.e.
		according	g to	the treatm	ent ac	tually	received	d).	

Intention-to-treat (ITT) Includes all subjects who were randomized based on the as randomized principle (i.e. according to the treatment they were randomized to).

Includes all subjects in the ITT who complete the visit 9 Per protocol (PP) months after baseline without any deviations considered to have substantial impact on the primary effectiveness outcome.

The ITT is the primary population for all effectiveness analyses. The primary effectiveness analysis will be repeated using the PP analysis set if there is at least a 10% difference in the number of subjects between the PP and ITT sets. Safety analysis is performed based on the safety population set. The disposition of subjects will be presented in tables and/or figures as appropriate.

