**Table 3. Major Protocol Deviations Causing Exclusion from Per-Protocol Population**

Major Deviation
Month 9 visit out of window by greater than 21 days or earlier than 7 days
Subject did not receive treatment as randomized
GDS live assessment by Treating Investigator not done at Month 9 (primary endpoint)
GDS live assessment by Treating Investigator not done at screening or baseline
GDS live assessment by Treating Investigator at baseline is not grade 2 or 3 (moderate or severe)
Prohibited concomitant treatments/procedures prior to Month 9 visit considered to have substantial impact on primary effectiveness outcome
Prohibited medical history, unstable medical history condition, or medical history condition that worsens prior to Month 9 visit considered to have substantial impact on primary effectiveness outcome

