## 2.4 Effectiveness Analysis

### 2.4.1 Datasets Analyzed

The ITT population is primary for all effectiveness analyses. The primary effectiveness analysis will be repeated using the PP analysis population if there is at least a 10% difference in the number of subjects between the PP and ITT populations.

 GALDERMA EST. 1981	Title 43USSA2112 Statistical Analysis Plan - Sculptra Decolletage US Pilot	Doc id MA-55694
---	--	---------------------------

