#### 2.4.2 Handling of Missing Data

Number of missing values will be summarized and reported as appropriate.

For the ITT analysis of the Treating Investigator GDS Responder rate at Month 9 after baseline (primary endpoint), missing values will be assumed to be missing due to lack of effect. Therefore, the primary method of imputation will use the baseline observation carried forward (BOCF) method. Impact of missing data on the primary endpoint will be evaluated by performing sensitivity analysis based on the observed cases, as well as worst-case and best-case imputation in the ITT set.

All other effectiveness endpoints will be evaluated based on the observed cases in ITT.

Descriptive statistics of all safety data will be performed on observed cases in the Safety population.

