#### 2.4.3 Primary Effectiveness Analysis

Responder rate for each treatment based on the GDS, as assessed live by the Treating Investigator at 9 months after baseline, will be the primary effectiveness endpoint. A responder will be defined as a subject with at least 1 grade improvement from baseline. The response rate will be calculated and presented with the 95% confidence intervals (calculated via Clopper-Pearson) for each treatment group and overall.

[figure not shown]

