## 2.8 Changes in the Analysis Planned in the Protocol

There are no changes to the analysis planned in the protocol.

GALDERMA EST. 1981	Title 43USSA2112 Statistical Analysis Plan - Sculptra Decolletage US Pilot	Doc id MA-55694
------------------------------	---	----------------------------------

2023-03-06 14:53

Effective date:

*Effective*

Version: 1.0

GALDERMA EST. 1981	Title 43USSA2112 Statistical Analysis Plan - Sculptra Decolletage US Pilot	Doc id MA-55694
------------------------------	--	---------------------------

CCI

2023-03-06 14:53

Effective date:

*Effective*

Version: 1.0

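### Do the two per-protocol triggers in SAP 2.2.3 and 2.4.1 leave it open whether the per-protocol analysis is run at 27 of 30?

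*SAP*

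**What the plan says.** Three places set the condition for repeating the primary analysis in the PP population.

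- SAP 2.2.3 states the condition as "If the PP population contains less than 90% of the subjects in the ITT" and the consequence as "a sensitivity analysis of the primary effectiveness endpoint will be performed based on the PP population". It names ITT as the base.
- SAP 2.4.1 makes ITT primary for effectiveness and repeats the primary analysis in PP "if there is at least a 10% difference in the number of subjects between the PP and ITT populations". It names no base.
- Protocol 9.2 (Analysis populations) has the rule of SAP 2.4.1: "if there is at least a 10% difference in the number of subjects between the PP and ITT sets".

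SAP 2.8 declares: "There are no changes to the analysis planned in the protocol". SAP 2.1 lets the SAP override the protocol's statistical sections. That does not choose between two sentences that are both in the SAP.

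For the primary endpoint, SAP 2.4.2 imputes missing Month 9 values by baseline observation carried forward. It adds, without any trigger: "Impact of missing data on the primary endpoint will be evaluated by performing sensitivity analysis based on the observed cases", together with worst-case and best-case imputation in the ITT set. The planned size is approximately 30, not based on a calculation (SAP 2.7.1).

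**The concern.** A trigger for a sensitivity analysis should give one answer for every possible data set. Here a strict and an inclusive inequality govern the same table, and they part at 27 of 30, which is the planned size with three exclusions. The study is open-label, and the primary endpoint is rated live by the Treating Investigator. Some PP exclusions in SAP Table 3 also rest on a judgement of substantial impact. If the two sentences conflicted, whether the PP table appeared could depend on which one the analyst happened to apply. At stake would be one supportive table of the Month 9 responder rate, not the primary result.

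**Working it through.** **Inputs.** N = number in ITT (all randomised; approximately 30, SAP 1.1.2). k = number excluded from PP, so PP = N − k.

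**Rules.**
- Rule A (SAP 2.2.3): PP/N < 0.90, which is k/N > 0.10.
- Rule B (SAP 2.4.1 and Protocol 9.2), ITT as base: k/N ≥ 0.10.

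**Nesting.** If k/N > 0.10 then k/N ≥ 0.10, so A implies B. The rules can differ only where k/N equals 0.10 exactly, which needs N to be a multiple of 10.

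**At N = 30.**

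| PP | PP/N | k/N | Rule A | Rule B |
|---|---|---|---|---|
| 26 | 86.7% | 13.3% | fires | fires |
| 27 | 90.0% | 10.0% | does not fire | fires |
| 28 | 93.3% | 6.7% | does not fire | does not fire |

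For N = 26 to 35 this is the only point of difference. With 28, 29, 31 or 32 randomised there is none.

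**If PP were the base in 2.4.1.** The rules would also part at 28/31 (3/28 = 10.7%), 29/32 (3/29 = 10.3%) and 30/33 (3/30 = 10.0%). This reading is strained: 2.2.3 names ITT as the base, and PP is defined as a subset of ITT. It would not alter the answer. Because k/PP is never smaller than k/N, rule A still implies rule B.

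**Chance of landing on the point.** The documents give no exclusion rate. Assume exactly 30 are randomised and each is excluded independently with probability p. Then P(k = 3) = 4060 × p³ × (1 − p)²⁷:
- p = 0.05: 0.127
- p = 0.10: 0.236
- p = 0.15: 0.170

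These hold only if N is exactly 30. Since N is approximate, the unconditional chance is lower.

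**What happens at the point.** SAP 2.2.3 says when the analysis will be done. It does not say that it will be done only then. At 27 of 30, 2.4.1 and Protocol 9.2 require the table and 2.2.3 is silent, so producing it complies with all three.

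**What is produced regardless.** For the ITT primary analysis, SAP 2.4.3 states: "The response rate will be calculated and presented with the 95% confidence intervals (calculated via Clopper-Pearson) for each treatment group and overall". The three missing-data analyses of 2.4.2 also run at any PP count. None of them uses either trigger.

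**The case for a change.** The best case for a change has three parts.

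1. A trigger is normally read in both directions, since a threshold that does not also say when to stop has little purpose. On that reading the two SAP sections do disagree at 27 of 30. This stands as a comment on drafting. The plan still settles it: SAP 2.8 declares no departure from the protocol, and only the 2.4.1 wording agrees with Protocol 9.2.

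2. The observed-case analysis does not replace the PP table. This is correct. Six of the seven rows of SAP Table 3 can exclude a subject who has a Month 9 GDS, for example "Month 9 visit out of window by greater than 21 days or earlier than 7 days". Only the row on a missing Month 9 GDS cannot. The PP table can also differ visibly from ITT. With r responders among 30, removing three non-responders moves the pooled rate by r/27 − r/30 = r/270, at most 27/270 = 10 percentage points. That is a reason to run the table at 27 of 30, which 2.4.1 already requires.

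3. The trigger is a pooled count, while results are shown by group. With an assumed 15 per arm, two exclusions in one arm leave 13/15 = 86.7% there but 28/30 = 93.3% overall. Neither rule fires, so this case says nothing about the mismatch. No document promises a per-arm trigger. SAP 2.3.1 already reports PP numbers by treatment group, and 2.3.2 summarises the reasons for exclusion, so an imbalance would be seen. Running the PP table always would be a matter of preference and would depart from Protocol 9.2.

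On discretion, exclusions are documented before database lock and the trigger is then a count. The judgement that remains is who is excluded, and aligning the two wordings would not touch that.

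**Conclusion.** The inconsistency is real but clerical: one nominal cut-off written once as strict and once as inclusive. With ITT as the base, it affects a single combination near the planned size, 30 randomised with 27 in PP. There the inclusive rule governs without strain, because it contains the other rule and matches the protocol. Applying 2.4.1 gives one answer at every count. SAP 2.1 and 2.1.2 also allow further supportive analyses without an amendment, so nothing prevents the table from being produced.

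Aligning the sentences would leave the primary ITT estimate, its Clopper-Pearson interval and the three missing-data analyses exactly as they are. The conclusion rests on ITT being the base, as 2.2.3 states. It would be the same with PP as the base. The wording could be tidied if the SAP were reopened for another reason, but nothing in the results depends on it.

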## 2.3 Study Subjects

Demographic endpoints and subject characteristics will be summarized using descriptive statistics by treatment group and overall based on the ITT population using observed cases. There are no planned inferential statistical analyses of demographic endpoints or subject characteristics.

### 2.3.1 Subject Disposition

The number of subjects screened will be shown in total and by study site.

The number of subjects in each study population (i.e., ITT, PP, and Safety) will be summarized by study site and in total (by treatment group and overall).

The disposition of subjects will be presented by treatment group, and in total, including numbers of subjects who were completed and withdrawn (including primary reason for withdrawal). These numbers will also be presented by study site.

The number of subjects expected, completed, withdrawn, and missed will be summarized by scheduled visit, using the following definitions:

[figure not shown]
- Expected = all subjects at screening minus subjects who have withdrawn up to that visit.
- Completed = subjects who showed up at that visit.
- Withdrawn = all subjects who have withdrawn up to that visit (cumulative).
- Missed = expected subjects minus completed subjects.

The end of study status will be listed for all subjects (both completed and withdrawn) individually, including at least subject number, end of study date, and last visit performed. In addition, reason for withdrawal will be provided for withdrawn subjects.

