3. STUDY DESIGN

3.1 Overall design

This is a prospective study to evaluate the safety and effectiveness of Sculptra for correction of wrinkles in the décolletage area.

Approximately 30 subjects will be enrolled in the study and randomized 1:1 to receive either Sculptra reconstituted with 8 mL SWFI with the addition of 1 mL 2% lidocaine hydrochloride (HCl) or Sculptra reconstituted with 17 mL SWFI with the addition of 1 mL 2% lidocaine HCl. Subjects will be stratified by GDS severity score (moderate or severe) and study center.

Eligible subjects will perform a screening visit and baseline visit; these visits may be combined, if appropriate. Eligible subjects will be offered treatment with Sculptra in four sessions spaced one month (+2 weeks) apart.

Subjects will be injected with Sculptra by the Treating Investigator at Baseline. Sufficient amount of product, as determined by the Treating Investigator, should be injected to achieve optimal correction, which is defined as at least a one grade improvement on the GDS and best correction that could be achieved as agreed upon by the Treating Investigator and the subject. Three additional treatment sessions may be performed if needed to achieve optimal correction, as determined by the Treating Investigator and subject. Treatment will stop when optimal correction has been achieved and subsequent visits will be follow-up visits.

Effective date: 2022-05-31 12:16

Print date:

Doc id

GALDERMA

initial treatment.

43USSA2112 CIP Sculptra Decolletage

MA-50966

2022-06-13 07:02

Safety follow-up assessments will also be conducted one month after each treatment (Visits 3a, 4a, 5a and 6). Safety and effectiveness data will be collected for up to 9 months following the

Study rationale and justification for design

The purpose of this study is to investigate the safety and effectiveness of *Sculptra* in two different reconstitution volumes for the correction of wrinkles in the décolletage area, with the objective of initiation of a pivotal study.

Evaluations will be performed by the Treating Investigator and the Subject. The intention is to improve the aesthetic appearance compared to baseline. Evaluations will be performed using the validated GDS, validated **CCI** and the GAIS (for Investigators and subjects).

GAIS improvement has been commonly accepted by the medical community in Europe and the United States as clinically meaningful indicator of global aesthetic improvement.

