4.3 Subject identification number

Prior to any study procedures being conducted, the subject must sign the ICF. Each subject who has signed the ICF will be assigned a screening number. Upon randomization, each subject will be assigned a subject identification number that will be allocated in ascending order within each center. A screen failure is a subject who signed the informed consent, but was never enrolled (i.e. was randomized and/or received treatment) in the study. For screen failures, the subject source documents should indicate which assessments have been made and the reason why the subject was determined to be a screen failure. A screen failure should not be re-entered in the study.

For the duration of the clinical study, each subject will be identified using the subject number for all documentation and discussion.

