Visit 4a, Treatment 3/Follow-up (1 month [+ 2 weeks] after Treatment 2) - all subjects

Assessments prior to treatment:

- Re-confirm eligibility criteria.
- Review for changes in concomitant therapies.
- Perform Urine Pregnancy test for all females of childbearing potential (prior to treatment, if applicable). Test result must be negative for the subject to be eligible for treatment.
- Obtain Photography.
- AE assessment.
- Collect subject diary from treatment 2 (if applicable, if a second treatment was administered).
- GAIS assessment Treating Investigator and Subject.
- GDS assessment Treating Investigator.
- Schedule the next on-site visit (1 month [+ 2 weeks] after Treatment 3). Treatment and assessments post-treatment, for subjects who receive a third treatment:
- Sculptra administration (optional).
- Evaluate the subject for post-treatment AEs Treating Investigator.
- Evaluate for device deficiencies.
- Dispense diary and instruct subject on daily diary completion. Remind subject to bring the diary to the next on-site visit. (If applicable, if a third treatment is administered.)

GALDERMA

Title
43USSA2112 CIP Sculptra Decolletage

MA-50966

8.8 Visit 5a, Treatment 4/Follow-up (1 month [+ 2 weeks] after Treatment 3) – all subjects

Assessments prior to treatment:

- Re-confirm eligibility criteria.
- · Review for changes in concomitant therapies.
- Perform Urine Pregnancy test for all females of childbearing potential (prior to treatment, if applicable). Test result must be negative for the subject to be eligible for treatment.
- Obtain Photography.
- CCI
- AE assessment.
- Collect subject diary from treatment 3 (if applicable, if a third treatment was administered).
- GAIS assessment Treating Investigator and Subject.
- GDS assessment Treating Investigator.

CCI

• Schedule the next on-site visit at Month 6 (+2 weeks) after Baseline.

Treatment and assessments post-treatment, for subjects who receive a fourth treatment:

- Sculptra administration.
- Evaluate the subject for post-treatment AEs Treating Investigator.
- · CCI

Doc id 43USSA2112 CIP Sculptra Decolletage GALDERMA **MA-50966**

- Evaluate for device deficiencies.
- Dispense diary and instruct subject on daily diary completion. Remind subject to bring the diary to the next on-site visit. (If applicable, if a fourth treatment is administered.)

8.11 Visit 6, Safety follow-up (1 month [+ 2 weeks] after Treatment 4) – for subjects that received treatment at Visit 5a.

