- Review for changes in concomitant therapies.
- AE assessment.
- Collect and review subject diary.

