#### 1.1.1 Study Design

This is a prospective open-label study to evaluate the safety and effectiveness of *Sculptra* for correction of wrinkles in the décolletage area.

Approximately 30 subjects will be enrolled in the study and randomized 1:1 to receive either *Sculptra* reconstituted with 8 mL Sterile Water For Injection (SWFI) with the addition of 1 mL 2% lidocaine hydrochloride (HCl) or *Sculptra* reconstituted with 17 mL SWFI with the addition of 1 mL 2% lidocaine HCl. Subjects will be stratified by Galderma Décolletage Scale (GDS) severity score (moderate or severe) and study center.

Eligible subjects will perform a screening visit and baseline visit; these visits may be combined, if appropriate. Eligible subjects will be offered treatment with *Sculptra* in four sessions spaced one month (+2 weeks) apart.

Subjects will be injected with *Sculptra* by the Treating Investigator at Baseline. Sufficient amount of product, as determined by the Treating Investigator, should be injected to achieve optimal correction, which is defined as at least a one grade improvement on the GDS and best correction that could be achieved as agreed upon by the Treating Investigator and the subject. Three additional treatment sessions may be performed if needed to achieve optimal correction, as determined by the Treating Investigator and subject. Treatment will stop when optimal correction has been achieved and subsequent visits will be follow-up visits.

CCI

[REDACTED] Safety follow-up assessments will also be conducted one month after each treatment (Visits 3a, 4a, 5a and 6). Safety and effectiveness data will be collected for up to 9 months following the initial treatment.

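### As written, the attendance rule in SAP 2.3.1 counts subjects who were not due at Visit 6 as having missed it

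*SAP*

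**What the plan says.** SAP 2.3.1 (Subject Disposition) plans a table of subjects expected, completed, withdrawn and missed at each scheduled visit. Its definitions include "Expected = all subjects at screening minus subjects who have withdrawn up to that visit" and "Missed = expected subjects minus completed subjects". Completed means those who came to the visit, and Withdrawn is a cumulative count. Withdrawal is the only thing subtracted to obtain Expected.

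The heading of Protocol 8.11 holds Visit 6, the safety follow-up one month after the fourth treatment, "for subjects that received treatment at Visit 5a". The other visible post-baseline headings in Protocol section 8 (Visits 3a, 4a, 5a, 7 and 8) cover everyone, for example "Visit 4a, Treatment 3/Follow-up (1 month [+ 2 weeks] after Treatment 2) - all subjects".

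Treatment beyond baseline depends on need. Protocol 3.1 states "Three additional treatment sessions may be performed if needed to achieve optimal correction", and SAP 1.1.1 states "Treatment will stop when optimal correction has been achieved and subsequent visits will be follow-up visits". Protocol 4.4 does not list reaching optimal correction among the reasons for withdrawal.

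**The concern.** A subject who reaches optimal correction before Visit 5a, or who is not treated there for another reason, stays in the study and has no Visit 6 to attend. The rule still puts her in Expected. She cannot be in Completed, so she falls into Missed.

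Visit 6 is where adverse events are assessed after the fourth session and where sites are told to "Collect and review subject diary". The natural use of its Missed count is to judge how complete that follow-up was. As defined, the count adds subjects who were never due to subjects who were due and did not come, and the row does not separate them.

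A second, smaller point concerns the starting set. Protocol 4.3 says "A screen failure is a subject who signed the informed consent, but was never enrolled". Such a subject was present at screening and has no later visits. Taken literally, the rule keeps her in Expected, and so in Missed, at every later visit unless she is classed as withdrawn.

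**Working it through.** The plan gives no figure to reproduce here, so the check applies its definitions to Visit 6.

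**Inputs**
- N = 30 randomised: the approximate planned number in SAP 1.1.1. Screen failures are set to zero at first.
- w = subjects withdrawn by Visit 6. Not given; assumed.
- k = subjects not withdrawn and not treated at Visit 5a. Not given; possible range 0 to 30.
- m = subjects due at Visit 6 who did not attend. Not given; assumed.
- Subjects who are not due do not attend.

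**Rule as written**
- Expected = N − w
- Completed = N − w − k − m
- Missed = (N − w) − (N − w − k − m) = k + m

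**Counting only subjects who are due**
- Expected = N − w − k
- Completed = N − w − k − m
- Missed = m

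The excess is k for any number of withdrawals. It is zero only if every remaining subject is treated at Visit 5a.

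**Illustrations with m = 1 (all values of k and w are assumptions)**

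| w | k | As written: Missed / Expected | Due subjects only: Missed / Expected |
|---|---|---|---|
| 0 | 0 | 1/30 = 3.3% | 1/30 = 3.3% |
| 0 | 6 | 7/30 = 23.3% | 1/24 = 4.2% |
| 0 | 15 | 16/30 = 53.3% | 1/15 = 6.7% |
| 0 | 24 | 25/30 = 83.3% | 1/6 = 16.7% |
| 2 | 6 | 7/28 = 25.0% | 1/22 = 4.5% |

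The SAP asks for numbers of subjects in this table. The percentages, with Expected as denominator, are added here only to show scale.

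**Screen failures.** With s screen failures not classed as withdrawn, Expected becomes N + s − w. With N = 30, w = 0 and everyone attending the baseline visit, s = 5 gives Expected 35 and Missed 5 in that row; s = 10 gives 40 and 10. At Visit 6 the count becomes s + k + m.

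**The case against.** The strongest reply is that this has little consequence. One row of a descriptive table is affected. The SAP states no purpose for that row, and a reader can rebuild the right figure by taking the number treated at the fourth session from the treatment administration tables of SAP 2.5.1 and, allowing for any who withdrew before Visit 6, subtracting those who attended. That is correct and keeps the point minor. It does not make the stated formula right.

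A second reply is that material not visible here may deal with it. SAP 2.1.2 places table formats in a companion document, and the schedules of assessments and parts of Protocol section 8 cannot be read. A footnote or a visit-specific rule may exist. One could also read a scheduled visit as scheduled for the individual subject, since at Visit 5a the site books Month 6 as the next visit. But SAP 2.3.1 writes out its formula, starts it from the whole screened group and removes only withdrawals. A programmer who follows it gets k + m, and no visible text says otherwise.

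A third reply is that k and m are unknown and that the range for k includes no effect. This stands: the size cannot be stated, only its form.

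A reader might go further and infer that the table would show a spurious difference between the 8 mL and 17 mL arms. With 15 per arm, no withdrawals, no true misses and an assumed k of 3 and 9, it would show 3/15 = 20% and 9/15 = 60% missed; with k = 6 in each arm it would show 40% in both. The documents support neither pattern. The sentence on attendance by visit does not itself ask for a split by arm; that follows only from the general statement in SAP 2.4.6.

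**Conclusion.** The point holds as a flaw in a definition. At Visit 6 the rule returns k + m where the number missed is m, because it ignores the restriction in Protocol 8.11. The excess k is unknown (0 to 30 of about 30), and every percentage above rests on assumed values. The algebra assumes that subjects who are not due do not attend; any who did would reduce the excess.

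The effect stops there. Among the visits that can be read, Visit 6 alone has such a condition: treatment is optional at Visits 3a, 4a and 5a, but attendance is due for everyone. It would be wrong to infer that effectiveness results, adverse event counts, analysis populations or the Month 9 imputation are affected, since none of them uses this table. It would also be wrong to infer that safety follow-up will actually be incomplete; the problem is in how attendance is counted. The screen-failure reading is literal and secondary, and would inflate the later rows by the number of screen failures. Correcting the rule is worthwhile but not critical.

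**What to change.** Replace the definitions in SAP 2.3.1 with:

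> For visits after screening, Expected = randomised subjects who have not withdrawn by that visit and for whom the visit is due under the protocol (Visit 6: only subjects treated at Visit 5a). Completed = Expected subjects who attended. Missed = Expected minus Completed.

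Keep Withdrawn as the cumulative count, shown separately and not subtracted again. Report the screening row as number screened and number of screen failures.

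The warning about subtracting again matters. Suppose 30 subjects are randomised, 2 withdraw before Visit 5a, 6 of the rest are not treated there, and 1 due subject does not come. Then 30 − 2 − 6 = 22 are treated and 21 attend. Taking the cumulative withdrawals off the treated group would give 22 − 2 = 20 expected and 20 − 21 = −1 missed. The wording above gives 22 expected, 21 completed and 1 missed.

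The cost is one SAP amendment, which SAP 2.1 requires for a change before database lock. It needs no new data and no extra table. A footnote in the table formats would avoid the amendment under SAP 2.1.2, but would leave the written definition uncorrected.
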